9.1 Clinical Assessments

9.1.1 Concomitant Medications

Inapplicable, participants should be healthy.

9.1.2 Demographics

Demographic information (date of birth, gender, income, education, professional status, and social status) will be recorded at screening.

9.1.3 Medical History

Relevant medical history will be recorded at Screening.

9.1.4 Physical Examination

A complete physical examination will be performed by co-investigator who is a physician at Visit 1. Qualified staff (MD, NP, RN, and PA) may complete the abbreviated physical exam at next visit.

9.1.5 Vital Signs

Body temperature, blood pressure, pulse and respirations will be performed after resting for 5 minutes at Visits 1 & 2.

9.1.6 Oximetry

Inapplicable

9.1.7 Spirometry

Inapplicable

9.1.8 Other Clinical Procedures

Inapplicable

9.1.9 Adverse Events

Information regarding occurrence of adverse events will be captured throughout the study. Duration (start and stop dates and times), severity/grade, outcome, treatment and relation to the supplementation will be recorded on the case report form (CRF).

9.2 Clinical Laboratory Measurements (include sections as appropriate)**9.2.1 Hematology**

Inapplicable

9.2.2 Blood Chemistry Profile

The blood analysis including glycated hemoglobin (H_{A1c}) and lipid profile (TC, HDL-C, and TG). Other blood analysis include: LPS, Aspartate Transaminase (AST), Alanine transaminase (ALT), superoxide dismutase (SOD), catalase, and glutathione peroxidase (GPx).

9.2.3 Pregnancy Test

Inapplicable

9.2.4 Urinalysis

Inapplicable

9.3 Pharmacokinetic Measurements

All analyses will be done in the CBCD, KSU using colorimetric method. Regular blood analysis will be taken at baseline and at the end of the study, then are kept into plan red covered tubes. All blood samples will be centrifuged (3500×5 mins) to separate serum samples. All tubes should be placed vertically for 45 minutes until the sample is completely coagulated, then transported to CBCD, KSU for further analysis.

9.4 Research Laboratory Measurements (include sections as appropriate)

Inapplicable

9.4.1 Cell Count and Differential

Inapplicable

9.4.2 Sputum Cytokine Measurements

Inapplicable

10 EVALUATIONS BY VISIT

10.1 Visit 1 in the beginning of study:

1. Review the study with the subject and obtain written informed consent.
2. Assign the subject a unique screening number.
3. Record demographics data.
4. Record medical history, including:
 - Stability of weight in the last three months prior the study.
 - Having any of the following diseases: Thyroid disorders, Diabetes type-1, Diabetes type-2, (Any type of disease) Cancer, Neurological disorders, psychiatric disorders, or other.
 - Having any of weight loss surgeries.
 - Enrolling in any diet during the past three weeks.
 - Taking antibiotics in the past 3 weeks.
 - Taking any probiotic supplements regularly for the past 3 months.
 - For ladies:
 - Are you planning to become pregnant in the next three months?
 - Are you taking any hormonal therapy?
5. Perform a complete physical examination.
6. Explain the possible side effect.
7. Perform and record results of blood pressure testing.
8. Collect blood for clinical laboratory.
9. Allocation process which includes randomizing the participants in two groups and allocation concealment.
10. Taking food frequency record for probiotics & prebiotics.
11. Taking 24-hour record.

12. Taking anthropometric measurements.
13. Taking physical activities.

10.2 Visit 2 at the end of the study (3 months length)

1. Perform an abbreviated physical examination
2. Perform and record results of blood pressure testing.
3. Collect blood for clinical laboratory.
4. Taking 24-hour record
5. Taking anthropometric measurements.
6. Taking physical activities.

10.3 Early Withdrawal Visit

1. Record any Adverse Experiences and/or review subject diary for adverse experiences and exclusionary medication use.
2. Record changes to concomitant medications.
3. Perform complete physical examination.
4. Perform and record vital signs.

11 ADVERSE EXPERIENCE REPORTING AND DOCUMENTATION

11.1 Adverse Events

In general, using probiotic products may cause mild bowel discomfort and diarrhea in the first few days or maximum one week for some people. All these symptoms will disappear later.

AE Severity

Probiotic products are considered over the counter drugs (OTC) which don't require doctor's prescription. Many clinical trials proved that Hexbio product doesn't cause any AE severity, that clearly explained in investigator's brochure. However, participant can stop participating at any time, recording reasons as possible.

AE Relationship to Study Drug

AE include possible bowel discomfort and mild diarrhea.

11.2 Serious Adverse Experiences (SAE)

Using probiotic products doesn't cause any SAE.

11.2.1 Serious Adverse Experience Reporting

Probiotic products are safe, however, if there are any SAEs, they will be documented (whether related to study drug or not). The collection period for all SAEs will begin after informed consent is obtained and end after procedures for the final study visit have been completed.

In accordance with the standard operating procedures and policies of the local Institutional Review Board (IRB), the site investigator will report SAEs to the IRB.

11.3 Protocol Defined Important Medical Findings Requiring Real Time Reporting

Inapplicable

12 DISCONTINUATION AND REPLACEMENT OF SUBJECTS

12.1 Early Discontinuation of Study Drug

A subject may be discontinued from study treatment at any time if the subject, the investigator, or the Sponsor feels that it is not in the subject's best interest to continue. The following is a list of possible reasons for study treatment discontinuation:

1. Subject withdrawal of consent (or assent)
2. Subject is not compliant with study procedures
3. Adverse event that in the opinion of the investigator would be in the best interest of the subject to discontinue study treatment
4. Protocol violation requiring discontinuation of study treatment
5. Lost to follow-up
6. Sponsor request for early termination of study
7. Positive pregnancy test (females)

If a subject is withdrawn from treatment due to an adverse event, the subject will be followed and treated by the Investigator until the abnormal parameter or symptom has resolved or stabilized.

All subjects who discontinue study treatment should come in for an early discontinuation visit as soon as possible and then should be encouraged to complete all remaining scheduled visits and procedures.

All subjects are free to withdraw from participation at any time, for any reason, specified or unspecified, and without prejudice.

Reasonable attempts will be made by the investigator to provide a reason for subject withdrawals. The reason for the subject's withdrawal from the study will be specified in the subject's source documents.

12.3 Withdrawal of Subjects from the Study

A subject may be withdrawn from the study at any time if the subject, the investigator, or the Sponsor feels that it is not in the subject's best interest to continue.

All subjects are free to withdraw from participation at any time, for any reason, specified or unspecified, and without prejudice.

Reasonable attempts will be made by the investigator to provide a reason for subject withdrawals. The reason for the subject's withdrawal from the study will be specified in the subject's source documents. As noted above, subjects who discontinue study treatment early (i.e., they withdraw prior to Visit 2) can have an early discontinuation visit.

12.4 Replacement of Subjects

Subjects who withdraw from the study treatment will not be replaced.

Subjects who withdraw from the study will not be replaced.

13 PROTOCOL VIOLATIONS

A protocol violation occurs when the subject, investigator, or Sponsor fails to adhere to significant protocol requirements affecting the inclusion, exclusion, subject safety and primary endpoint criteria. Protocol violations for this study include, but are not limited to, the following:

1. Failure to meet inclusion/exclusion criteria
2. Use of a prohibited concomitant medication
3. Not follow the role, (for example do not follow the health guideline).
4. Not use the probiotic according to the description.

Failure to comply with Good Clinical Practice (GCP) guidelines will also result in a protocol violation. The Sponsor will determine if a protocol violation will result in withdrawal of a subject.

When a protocol violation occurs, it will be discussed with the investigator and a Protocol Violation Form detailing the violation will be generated. This form will be signed by a Sponsor representative and the Investigator. A copy of the form will be filed in the site's regulatory binder and in the Sponsor's files.

14 DATA SAFETY MONITORING (OPTIONAL SECTION – INCLUDE WHEN APPROPRIATE)

Inapplicable

15 STATISTICAL METHODS AND CONSIDERATIONS

The primary outcome of this study is the difference in waist circumference between groups after 12 weeks of supplementation. The analysis of this study will include all the patients using intention to treat (ITT) methodology. Waist circumference of two groups after 12 weeks of supplementation will be examined for statistical significant using repeated measures ANOVA.

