5 CRITERIA FOR EVALUATION

5.1 Primary Efficacy Endpoint

The primary outcome is the relative change in WC measurement from baseline to end-of-treatment.

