15.6 Sample Size and Randomization

The study population depends on the study result of Gomes and his colleagues who used the G-Power software (version 3.0.10) to calculate the sample size. The primary outcome in that study is the difference in waist circumference between groups. The power calculation requires 17 participants in each group (95% power; 5% type I error) to detect a difference in waist circumference (Gomes et al, 2018). In this study, to avoid any later drop-off, both groups will be set to have 45 participants.

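### ITT on all patients is promised, but nothing says how a missing Visit 2 waist is handled; by default the named methods give a completer comparison that would be reported as ITT

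*Combined protocol and SAP*

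**What the plan says.** **Population.** The synopsis and section 15 both promise: "The analysis of this study will include all the patients using intention to treat (ITT) methodology". Section 15.1 says that each analysis takes in every eligible subject, without defining the term.

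**Method.** Section 15 continues: "Waist circumference of two groups after 12 weeks of supplementation will be examined for statistical significant using repeated measures ANOVA". Sections 15.3 and 15.4 each say only ANOVA. Section 5.1 words the endpoint differently: "The primary outcome is the relative change in WC measurement from baseline to end-of-treatment". No part of section 15 mentions imputation, a likelihood-based model, a missing-data assumption or a sensitivity analysis.

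**When waist is taken.** Sections 10.1 and 10.2 each list "Taking anthropometric measurements". The early withdrawal visit (10.3) has four items, ending with "Perform and record vital signs"; none is anthropometric. The Appendix 1 schedule lists height and weight but neither waist nor hip.

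**Expected loss.** Section 15.6: "In this study, to avoid any later drop-off, both groups will be set to have 45 participants". Section 12.4 rules out replacement.

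**Follow-up after stopping.** Section 12.1 says that those who stop treatment should attend an early visit and then "should be encouraged to complete all remaining scheduled visits and procedures". Section 12.3 says that "subjects who discontinue study treatment early (i.e., they withdraw prior to Visit 2) can have an early discontinuation visit". Section 13 leaves it to the Sponsor whether a protocol violation leads to withdrawal, and its list of violations includes not taking the product as described.

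**The concern.** An ITT comparison needs an outcome, or a stated substitute for it, for everyone randomised. This plan has one post-baseline waist per person and no substitute. If the analyst simply runs the named test, those without a Visit 2 waist drop out and the result still carries the ITT label.

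That comparison is biased if the amount of loss, or the reasons for it, differ between arms and relate to waist change. Bowel discomfort in the first days, which section 11.1 anticipates, and withdrawal for not taking the product are routes by which loss could depend on the arm or on adherence. The documents do not say that either will happen.

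Timing matters. A Visit 2 waist that nobody sought cannot be recovered later, and a missing-data method chosen after the codes are known invites doubt about the choice.

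**Working it through.** **1. The plan's own figure.** Section 15.6 gives 17 per group (95% power, 5% type I error), raised to 45. The 17 cannot be reproduced, because no waist difference, SD or sidedness is stated. Solved backwards with a t-test, it implies a standardised difference of 1.28 (two-sided) or 1.15 (one-sided); the documents give nothing to compare this with. The margin is 45 − 17 = 28 per group, and 28/45 = 62%. This is the loss the count could absorb before falling below 17. It is not a rate that the plan expects or accepts, and it says nothing about bias.

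**2. What the named methods do with a missing value.** Each version of the primary analysis needs the Visit 2 waist:

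| Version | Where | Needs Visit 2 waist |
|---|---|---|
| Group difference at 12 weeks | Synopsis, 15 | Yes |
| Relative change from baseline | Synopsis, 5.1 | Yes |
| Repeated measures ANOVA, standard form | Synopsis, 15 | Yes |
| ANOVA | 15.3 | Yes |

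With two time points, the group-by-time test in a standard repeated measures ANOVA is the squared t-test on change among participants with both values. In simulated data with 65 of 90 complete, F was 0.0330 by both routes.

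**3. Size of bias, illustration only.** Let L1 and L0 be the numbers lost on active and placebo, and g1 and g0 how much worse the lost do than the retained, in SDs of the analysed waist measure among the retained. Every L and g is assumed. The retained mean flatters each arm by L × g / 45, so

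bias = (L1 × g1 − L0 × g0) / 45.

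False-positive rate with no true effect: two-sided 5% t-test on n1 = 45 − L1 and n0 = 45 − L0, noncentrality = bias / √(1/n1 + 1/n0). With equal gaps g:

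| Lost, active v placebo | g | Bias (SD) | Noncentrality | False-positive rate |
|---|---|---|---|---|
| 9 v 9 | 0.5 or 1 | 0 | 0 | 5.0% |
| 9 v 5 | 0.5 | 4 × 0.5/45 = 0.044 | 0.044/0.230 = 0.19 | 5.4% |
| 9 v 5 | 1 | 4 × 1/45 = 0.089 | 0.089/0.230 = 0.39 | 6.7% |
| 14 v 5 | 0.5 | 9 × 0.5/45 = 0.100 | 0.100/0.239 = 0.42 | 7.0% |
| 14 v 5 | 1 | 9 × 1/45 = 0.200 | 0.200/0.239 = 0.84 | 13.1% |

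Losing 5 v 14 gives the same sizes with the opposite sign. Equal loss is not safe if the gaps differ: 9 v 9 with a gap of 0.5 on active only gives 9 × 0.5/45 = 0.10 SD.

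**4. Whether imputation alone would cure it.** In a simulation of 14 v 5 lost with a gap of 1 SD beyond what baseline explains and no true effect, the bias was 0.197 SD by complete cases and 0.197 SD after multiple imputation by arm from baseline waist (correlation of estimates 0.99). At a gap of 0.5 it was 0.107 and 0.106. Imputing from baseline alone keeps everyone in the analysis but leaves the bias where it was.

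**5. What a sensitivity analysis would show.** Making imputed values worse by d1 and d0 moves the arm difference by (L1 × d1 − L0 × d0)/45. With 9 v 5 lost, a shift d on active only moves it by 9d/45 = 0.20d; the same shift in both arms moves it by 4d/45 = 0.089d.

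**The case against.** **The promise could still be kept.** A reader might infer that the named method cannot deliver ITT. The text does not go that far: imputing the Visit 2 waist and then running the ANOVA is compatible with section 15. What stands is that no such step is stated and that the default drops incomplete pairs.

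**Follow-up is partly covered.** Section 12.1 encourages people to complete their visits after stopping treatment, which should reduce missing data. A reader might take 12.3 to equate stopping the product with leaving the study. But that sentence refers back to 12.1 and sits under study withdrawal, so it may describe only those who leave. The firm discrepancy is narrower: 12.1 says those who stop should come to the early visit, and 12.3 says they can. Likewise, section 13 does not say whether withdrawal for a violation is from treatment or from the study, and 12.1 lists a violation as a reason for stopping treatment only. Loss of the Visit 2 waist by this route is possible but not established.

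**Section 15.1 may be harmless.** Section 4.1 admits only people who meet the criteria, so eligible could mean everyone entered. It is loose wording, because section 13 foresees eligibility failures, but it is not clearly a different set.

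**The numbers are assumed.** This stands in full. No dropout rate, gap or SD is in the documents, and moderate imbalance (9 v 5) moves the false-positive rate little.

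**Conclusion.** The gap is real: ITT on all patients is promised, no rule covers a missing Visit 2 waist, and by default the result is a completer comparison under an ITT label. Confidence in that is high, and all of section 15 is present in the public text, so the gap does not come from removed pages.

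The size and direction of any bias are unknown. A reader might conclude that the trial will favour the probiotic. The documents do not support this, since the sign depends on which arm loses more people and why. On the assumed cases with equal gaps, bias runs from nil (equal loss) to 0.20 SD either way (14 v 5 or 5 v 14, gap 1 SD). It is small unless loss is clearly unequal or the gaps differ between arms. The point should therefore be fixed, but it does not by itself undermine the trial.

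**What to change.** 1. Reconcile 12.1, 12.3 and 13 so that a Visit 2 waist is sought at the planned date from every randomised participant who has not withdrawn consent, including those who stopped the product or had a violation. This concerns data collection only and changes nothing about when treatment stops. It is needed before enrolment.
2. Add waist, hip and weight to the early withdrawal visit (10.3), and waist and hip to Appendix 1. An early waist informs the 12-week value but does not replace it.
3. Replace 15.1 with all randomised participants, analysed as randomised.
4. Analyse Visit 2 waist adjusted for baseline waist, with a named missing-data method, fixed before unblinding, that uses any early-withdrawal waist.
5. Pre-specify one sensitivity analysis in which participants with a missing waist do worse, in either arm or both, over a stated range, for example from 0 up to a waist difference that the plan declares important. The plan would have to state that figure.

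Protection against bias comes mainly from items 1, 2 and 5. If none of this is done, the primary result should be labelled a completer analysis.

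Cost: protocol and SAP wording, some effort to bring participants back, and modest programming. No extra visit is needed.

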PRIMARY OBJECTIVE	Study the anti-obesity effect of consuming multi-Strain probiotic supplementation on weight loss for overweight and obese adults.
SECONDARY OBJECTIVES	
 1. Investigate the effect of probiotics on reducing Lipopolysaccharides LPS. 2. Determine the effect of probiotics on liver functions. 3. Study the association between probiotics and food intake. 4. Evaluate the role of gender difference in response to probiotic.
NUMBER OF SUBJECTS	90
SUBJECT SELECTION CRITERIA	
Inclusion Criteria:
 
 1. Adult's male and female ages between 19 to 40 years. 2. BMI (in kg/m²) from 25 to 35, (WHO, n. d.) WC > 88 cm (women) or > 102 cm (men) (lean et al, 1995). 3. Stable body weight in the previous month of the trial. 
Exclusion Criteria:

	
 Participants who suffer from diseases and on treatment, such as immune system diseases or thyroid disorders. Pregnant women or who plans to be pregnant. Participants who had gastrointestinal surgery. Hormone replacement therapy. Participants who taking antibiotic. Participants who consume probiotic or prebiotic supplementation regularly.
TEST PRODUCT, DOSE, AND ROUTE OF ADMINISTRATION	
Product: (HEXBIO®) containing MCP® BCMC® strains Each sachet containing 3g / 90 billion CFU Oral consumption. Two sachets per day, by dissolving the sachet content in a glass of room-temperature water, one before breakfast and one before going to bed, for three months length.

CONTROL PRODUCT, DOSE AND ROUTE OF ADMINISTRATION	
The placebo sachets containing only the excipients, i.e., maize starch and maltodextrins. The placebo was indistinguishable in color, smell, and taste from the probiotic formulation. All participants will be asked to consume two sachets per day, one before breakfast and one before going to bed, after dissolving the content in a glass of room-temperature water.

DURATION OF SUBJECT PARTICIPATION AND DURATION OF STUDY	
Subjects will be on study for up to 3 months Screening: In the beginning of study Treatment: 3 months Follow-up: 3 months The total duration of the study is expected to be 6 months for subject recruitment and 6 for final subject follow-up.

PRIMARY ENDPOINT	
 The primary outcome is the relative change in WC measurement from baseline to end-of-treatment.

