SECONDARY ENDPOINTS	
 Other obesity-related outcomes included body weight, WC, and hip circumference (HC).
STATISTICS Primary Analysis Plan	
The primary outcome of this study is the difference in waist circumference between groups after 12 weeks of supplementation. The analysis of this study will include all the patients using intention to treat (ITT) methodology. Waist circumference of two groups after 12 weeks of supplementation will be examined for statistical significant using repeated measures ANOVA.

Rationale for Number of Subjects	The study population depends on the study result of Gomes and his colleagues who used the G-Power software (version 3.0.10) to calculate the sample size. The primary outcome in that study is the difference in waist circumference between groups. The power calculation requires 17 participants in each group (95% power; 5% type I error) to detect a difference in waist circumference (Gomes et al, 2018). In this study, to avoid any later drop-off, both groups will be set to have 45 participants.
---	--

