4 STUDY DESIGN

4.1 Study Overview

This is a single center, double-blind, placebo-controlled, randomized, trial. Subjects number will be 90 participants. Each subject will be administered a one dose of probiotic supplementation, two times per day, for three months, consisting each time of stable doses of active or placebo.

Subjects will be assigned to the treatment in random order. Evaluations will be taken at baseline and at the end of study.

Screening data will be reviewed to determine subject eligibility. Subjects who meet all inclusion criteria and none of the exclusion criteria will be entered into the study.

The following treatment regimens will be used:

- Experimental treatment is Hexbio sachet containing 3g / 90 billion CFU
- Placebo sachets containing only the excipients, i.e., maize starch and maltodextrins. The placebo was indistinguishable in color, smell, and taste from the probiotic formulation.

Total duration of subject participation will be three months. Total duration of the study is expected to be six months.

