5.2 Secondary Efficacy Endpoints

Other obesity-related outcomes included body weight, WC, and hip circumference (HC).

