5.4 Other Evaluations (include only if applicable)

Primary Efficacy Endpoint: The primary outcome is the relative change in WC measurement from baseline to end-of-treatment.

Secondary Efficacy Endpoints: Other obesity-related outcomes included body weight, WC, and hip circumference (HC).

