8 STUDY TREATMENTS

8.1 Method of Assigning Subjects to Treatment Groups

In allocation process, a randomization center will be involved in randomizing the participants in two groups, also there will be allocation concealment, according to the following steps:

- Hexbio company will provide sachets which only have alphabet Q or R.

- In the beginning of the study, participants will be given a unique number by the research phlebotomist.
- The randomization scheme will be computer generated in which all participants will be allocated (1:1) in two different groups, group Q and group R.
- After completing the intervention, a request letter will be sent to the company in order to unblind the study.
- Then the company lab will send an unblinding letter to inform us which alphabet is probiotic or placebo.

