8.3.3 Packaging and Labeling

Packaging: Study drug is supplied in cartons containing 1,200 single use sachets. The sachets will be packaged in sets of 10 enclosed within a transparent zipper bag. Six zipper bags will be contained in one plain box labeled with instruction for use and storage. Twenty plain boxes will be contained in each carton.

Labeling: Each **plain box of study drug (not carton)** will be labeled with the required FDA warning statement, the protocol number, a treatment number, the name of the sponsors, and directions for patient use and storage. Each sachet will be labeled with OA-R-01 or OA-Q-01 and Expiry date.

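### The primary outcome has two definitions and no stated tested term; the consequence is small between the change-type readings and large only if the 12-week sentence is applied literally

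*Combined protocol and SAP*

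**What the plan says.** **Definition A.** The Primary Endpoint entry of the synopsis and section 5.1 state: "The primary outcome is the relative change in WC measurement from baseline to end-of-treatment". Section 5.4 repeats this under its own label. None of them gives a formula for the word relative.

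**Definition B.** The Statistics entry of the synopsis and the opening of section 15 state: "The primary outcome of this study is the difference in waist circumference between groups after 12 weeks of supplementation".

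**The test.** Both Definition B places continue: "Waist circumference of two groups after 12 weeks of supplementation will be examined for statistical significant using repeated measures ANOVA". Section 15.3, on the primary endpoint, consists of the single word ANOVA. No section names the tested term (group, time or group-by-time) or a baseline covariate.

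**Visits.** Section 4.1 allows two measurement times: "Evaluations will be taken at baseline and at the end of study".

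**Secondary list.** WC appears again among the secondary endpoints in the synopsis and in sections 5.2 and 5.4.

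**Group letters.** Section 8.1 says: "The randomization scheme will be computer generated in which all participants will be allocated (1:1) in two different groups, group Q and group R". Section 8.3.3 adds: "Each sachet will be labeled with OA-R-01 or OA-Q-01 and Expiry date".

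**The concern.** Definitions A and B are different variables, and both stand in the current text; the synopsis alone contains both. The named test does not decide between them. The sentence in section 15 points to a single time, 12 weeks, yet a repeated measures analysis needs both visits. With two visits, its group-by-time term is the test of absolute change, which is neither definition exactly.

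Two analysts could therefore each follow the protocol and report different primary p-values. The timing of the choice matters because the arms carry open letters. A two-sided Q-versus-R p-value can be computed under any reading before the company reveals which letter is active. A choice made just before unblinding could thus come after the results are known.

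**Working it through.** **The plan's own figure.** Section 15.6 takes 17 per group (95% power, 5% type I error) from an earlier study and plans 45 per group. It gives no difference, SD, sidedness or test. The 17 therefore cannot be reproduced, and it does not show which definition is meant.

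**Inputs.** From the documents: two visits, 1:1 allocation, n = 45 per arm, 5% type I error. Assumed: all 45 analysed, two-sided test, WC mean 100 cm and SD 10 cm at both visits, bivariate normal, r = 0.5 to 0.9, and true effects of 0, 3 and 5 cm. Relative change is taken as 100 × (end − baseline)/baseline.

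**Step 1: what group-by-time tests.** With two visits the contrast is (end − baseline) in Q minus (end − baseline) in R. Its F statistic is the square of the t statistic on absolute change.

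**Step 2: standard error of the effect, in SD units.**
- 12-week only: √(2/n) = √(2/45) = 0.211
- Absolute change: √(4(1 − r)/n) = 0.211 at r = 0.5 and 0.094 at r = 0.9
- ANCOVA: √(2(1 − r²)/n) = 0.183 at r = 0.5 and 0.092 at r = 0.9

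**Step 3: noncentral-t power at 3 cm (0.3 SD).**

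| r | 12-week only | Absolute change | ANCOVA |
|---|---|---|---|
| 0.5 | 29.1% | 29.1% | 36.9% |
| 0.6 | 29.1% | 35.0% | 42.1% |
| 0.7 | 29.1% | 44.3% | 50.4% |
| 0.8 | 29.1% | 60.5% | 65.0% |
| 0.9 | 29.1% | 88.2% | 89.8% |

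At 5 cm the powers are 65% for 12-week only, 65% to 99.9% for change, and 77% to over 99% for ANCOVA.

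**Step 4: how often two readings disagree on significance (simulation, 100,000 trials per setting).**

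| r | Relative v absolute change, 3 cm | 12-week only v relative change, 3 cm | 12-week only v relative change, 5 cm |
|---|---|---|---|
| 0.5 | 3.1% | 28.1% | 30.4% |
| 0.6 | 3.3% | 31.4% | 30.7% |
| 0.7 | 3.4% | 36.9% | 32.0% |
| 0.8 | 3.4% | 46.3% | 34.0% |
| 0.9 | 1.7% | 63.2% | 35.0% |

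Relative and absolute change also disagree in at most 3.4% of trials at 5 cm.

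**Step 5: direction of the disagreement at 3 cm.** At r = 0.5 it is about 14% each way. At r = 0.9 the 12-week test alone is significant in only about 2% of trials; the rest is the weaker test missing the effect (29% v 88% power).

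**Step 6: no true effect.** At least one of 12-week only and relative change is significant in 9.2–9.7% of trials. For relative or absolute change the figure is 5.5–5.6%.

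**Sensitivity.** With 36 per arm analysed (an assumed 20% loss), power at 3 cm is 24% for 12-week only, 24–80% for change and 31–82% for ANCOVA. The 12-week-only test disagrees with relative change in 25–61% of trials at 3 cm. Relative and absolute change disagree in at most 3.6%.

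**The case against.** The strongest reply is that the plan, read sensibly, points to change from baseline. Definition A is a change, and a repeated measures ANOVA on two visits most naturally yields the group-by-time term. Those two readings almost always agree. All the large figures need the 12-week-only reading, which fits the words repeated measures worst. This stands, and it limits the size of the point. It does not remove it, because Definition B taken literally is a 12-week comparison and no section rules that out.

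A reader might also infer that ANOVA in section 15.3 is a second, competing test. The documents do not support that. The word sits under a section that has just named repeated measures ANOVA, so shorthand is the natural reading. What is missing is the tested term.

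Finally, replacing relative change with ANCOVA on WC in cm is partly preference. The gain over change is modest at r = 0.9 (88% to 90%) and larger at r = 0.5 (29% to 37%). It is therefore a recommendation; the requirement is a single stated analysis.

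**Conclusion.** The concern holds with limited weight. The primary outcome has two definitions, relative change has no formula, and the tested term and any baseline covariate are unstated. Between relative and absolute change the consequence is small: at most about 3.4% disagreement. It is large only under the literal 12-week-only comparison, at 28–63% disagreement with relative change for a 3 cm effect. At high r that is mainly lost power; at r = 0.5 it runs equally both ways.

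Two stronger inferences are not supported. First, the 63% figure does not mean that the two definitions lead to opposing treatment claims: it is almost entirely one test missing an effect that the other finds. Second, the 9–10% false-positive rate is not a property of the plan. It arises only if the better of those two results is picked after seeing both. Nothing in the documents suggests that intent, and section 15.5 leaves all analysis to the end of the intervention.

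The mean, SD, correlation, effect sizes and completeness of data are assumptions. The conflict in the text does not depend on them.

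**What to change.** **Required.** In the synopsis (endpoint and statistics entries) and sections 5.1, 5.4, 15 and 15.3, state the same primary endpoint, one model and one tested term. Date the change before any outcome data are compared by the letters Q and R.

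**Recommended wording.** Primary endpoint: WC (cm) at the end-of-treatment visit. Analysis: ANCOVA with treatment and baseline WC; the tested term is treatment; report the adjusted mean difference with its 95% confidence interval, at a two-sided 5% level. Report relative change as supportive.

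**If relative change stays primary.** Define it by formula, for example 100 × (end − baseline)/baseline. Use that definition in the synopsis statistics entry and in section 15 as well, and name its one test.

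**Consequential edits.** If WC in cm becomes primary, remove WC from the secondary lists in the synopsis and in sections 5.2 and 5.4. In section 15.4, use the same baseline-adjusted model for weight and hip circumference.

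**Cost.** Protocol and SAP wording only. Sections 10.1 and 10.2 already schedule anthropometry at both visits, and relative change already needs WC at each, so no extra data, visits or participants are needed.

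The analysis set (section 15 against 15.1) and the handling of a missing end-of-treatment WC are separate points that this change does not settle.
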